Acute Oroantral Communication Closure: Resorbable Collagen Membrane vs. Buccal Advancement Flap Outcomes: A Clinical Trial

PCN/0022/KB1/94/20/21

12.02.2021

Study Protocol and Statistical Analysis Plan

Protocol Overview and Rationale

This investigator-initiated, prospective, non-randomized, parallel-group clinical study was designed to compare the clinical effectiveness and early radiographic healing associated with two surgical techniques for closure of acute oroantral communication (OAC) diagnosed within 24 hours after extraction of posterior maxillary teeth. The study was conducted at the Department of Dental Surgery, Faculty of Medical Sciences in Zabrze, Medical University of Silesia. The protocol was approved by the Institutional Review Board (PCN/0022/KB1/94/20/21), and all participants provided written informed consent prior to enrollment.

The study hypothesis was that minimally invasive closure using a resorbable heterogeneous collagen membrane would better preserve soft tissue architecture and reduce postoperative morbidity compared with the conventional Rehrmann buccal advancement flap, while maintaining comparable early bone healing.

Study Population and Enrollment

Consecutive adult patients presenting with acute OAC within 24 hours following extraction of a maxillary posterior tooth were screened for eligibility according to predefined inclusion and exclusion criteria. Twenty-four patients were enrolled; twenty completed the full 90-day follow-up and were included in the final analysis. The mean defect diameter was 3.5 ± 1.0 mm (range 2 to 5 mm), verified clinically and with limited-field CBCT on day 0.

Interventions and Standardization

Participants were assigned to one of two parallel treatment arms based on a predefined clinical protocol and the availability of the membrane technique at the time of treatment. Formal randomization and allocation concealment were not implemented.

All surgical procedures were performed by the same experienced oral surgeon to minimize operator-related variability. Preoperative preparation, socket debridement, smoothing of sharp bony margins, antibiotic prophylaxis, sinus precautions, analgesic recommendations, and follow-up schedules were standardized across both groups.

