Experimental arm: closure using submucosal placement of a resorbable heterogeneous collagen membrane (Creos Xenoprotect) stabilized with horizontal mattress sutures following limited mucoperiosteal elevation without vertical releasing incisions.

Control arm: closure using the classical Rehrmann buccal advancement flap involving trapezoidal full-thickness mucoperiosteal flap elevation with vertical releasing incisions and periosteal releasing incision to permit tension-free coronal advancement.

Follow-up Schedule and Data Collection

Clinical assessments were conducted at baseline (day 0) and on postoperative days 1, 7, 14, and 90. The final radiographic assessment using limited-field CBCT was performed at baseline and at 90 days.

Clinical measurements (vestibular depth, keratinized gingiva width, alveolar socket dimensions) were performed using a calibrated WHO periodontal probe by an independent

examiner blinded to the surgical procedure. Examiner calibration was performed prior to study initiation using repeated measurements in a subset of patients.

Radiographic measurements and region-of-interest (ROI) density analyses were conducted by two trained investigators using standardized protocols in Romexis (v6.4) and ImageJ (v1.53k). Discrepancies were resolved by consensus.

Outcome Measures

Primary endpoint:

- Change in vestibular depth from baseline to 90 days.

Secondary endpoints:

- Change in keratinized gingiva width.
- Change in alveolar socket dimensions.
- Postoperative pain intensity measured with the Visual Analogue Scale (VAS) at days 1, 7, and 14.
- Incidence of postoperative complications (swelling, hematoma, epistaxis, wound dehiscence, persistent communication, fistula formation, clinical sinusitis).
- Normalized bone density at the surgical site derived from CBCT.

Radiographic Density Methodology

Because CBCT gray values are not directly equivalent to absolute Hounsfield Units, density measurements were normalized to adjacent cortical bone within the same scan to reduce inter-individual variability and acquisition-related bias. Regions of interest were placed at three standardized vertical levels of the alveolus (crestal, mid-alveolar, and apical). The arithmetic mean of normalized values was used for statistical analysis.

Statistical Analysis Plan

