All analyses were performed using STATISTICA version 13.0. Continuous variables are presented as mean \pm standard deviation. Categorical variables are presented as counts and proportions.

Assumption testing:

- Normality assessed with the Shapiro–Wilk test.
- Homogeneity of variance assessed with Levene’s test.

Between-group comparisons:

- Independent-samples t test for normally distributed variables with equal variances.
- Mann–Whitney U test when parametric assumptions were violated.

Multiplicity control:

The primary endpoint retained a two-sided alpha of 0.05. Because multiple secondary endpoints were analyzed, Bonferroni correction was applied for secondary comparisons, and these results were interpreted as supportive.

Handling of missing data:

Only participants who completed the 90-day follow-up were included in the final per-protocol analysis. No imputation of missing values was performed.

Power considerations:

Given the final sample size ($n = 20$), the study was adequately sensitive for detecting large between-group differences in soft tissue outcomes but underpowered for moderate radiographic density effects. Therefore, CBCT density findings were prespecified as exploratory.

Bias Control Measures

- Single experienced surgeon to reduce procedural variability.
- Independent blinded clinical assessor.
- Dual-investigator radiographic analysis with consensus resolution.
- Standardized postoperative management in both arms.
- Objective probe-based measurements at predefined time points.

Safety Monitoring

Participants were monitored at each follow-up visit for adverse events, including infection, dehiscence, hematoma, epistaxis, persistent OAC, fistula formation, and signs of maxillary sinusitis. All complications were recorded prospectively. No serious adverse events related to the interventions were reported.

Ethical Considerations

The study complied with the Declaration of Helsinki and applicable institutional requirements. Participation was voluntary, and patients could withdraw at any time without affecting their treatment. Data confidentiality was maintained throughout the study.

Protocol Limitations

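### The only power statement, that 20 patients suffice for large soft-tissue differences, is unsupported, and wrong if large means the conventional 0.8 SD

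*Combined protocol and SAP*

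**What the plan says.** Under Power considerations, the SAP states that with the final 20 patients "the study was adequately sensitive for detecting large between-group differences in soft tissue outcomes". The same sentence contrasts this with CBCT density, for which the study is called underpowered for moderate effects. No other sample-size or power justification appears in the document.

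The inputs that bear on the claim are spread over several sections:

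- Study Population and Enrollment: "Twenty-four patients were enrolled; twenty completed the full 90-day follow-up and were included in the final analysis".
- Interventions and Standardization: "Participants were assigned to one of two parallel treatment arms based on a predefined clinical protocol", and on whether the membrane was available. There was no randomization, and no arm sizes are given.
- Multiplicity control: "The primary endpoint retained a two-sided alpha of 0.05". For the rest, "Bonferroni correction was applied for secondary comparisons, and these results were interpreted as supportive". The divisor is not stated.
- Outcome Measures: the primary endpoint is change in vestibular depth. The first secondary endpoint is "Change in keratinized gingiva width", which is also a soft-tissue outcome.
- Between-group comparisons: an independent-samples t test, or the Mann–Whitney test if its assumptions fail.

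**The concern.** The sentence assigns the design a power property without the quantities that would establish it: an effect size, an SD, a target power and the number in each arm. It also pairs large with moderate, which is the vocabulary of standardised effect sizes. Read that way, large is 0.8 SD, and 20 patients are far too few to detect it reliably.

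Two features add to the problem. The claim refers to soft-tissue outcomes in the plural, yet one is tested at 0.05 and another at a smaller Bonferroni level, so a single statement of sensitivity cannot describe both. It also uses the number who completed follow-up, so it describes what was achieved and is not a prospective justification of sample size.

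Interpretation is what is at stake. By naming only density as underpowered, the plan invites a reader to take a non-significant vestibular-depth or keratinized-width result as evidence that no large difference exists.

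**Working it through.** The plan gives no power figure, so there is nothing to reproduce. The check asks what 20 analysed patients can detect with the planned test.

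**Inputs from the documents.** Total analysed 20; two-sided alpha 0.05 for the primary endpoint; two-sample t test; Bonferroni correction for secondary endpoints.

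**Assumptions, with ranges.**

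- Large = 0.8 SD; effects up to 2.0 SD are also shown.
- Target power 80%.
- Split 10/10, the best case, with less even splits down to 6/14.
- Bonferroni divisor from 2 to 13. A divisor of 2 counts only keratinized width and socket dimensions. The list has five secondary bullets; leaving out density as exploratory gives 4. Counting every listed item separately gives 1 (keratinized width) + 1 (socket) + 3 (pain at days 1, 7 and 14) + 7 (complications) + 1 (density) = 13.

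**Formula.** Power = P(|T| > t_crit), where T is noncentral t with n1 + n2 − 2 degrees of freedom and noncentrality d × √(n1·n2/(n1 + n2)).

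**Primary endpoint, alpha 0.05.** With 18 degrees of freedom, t_crit = 2.101. At 10/10 and d = 0.8, the noncentrality is 0.8 × √(100/20) = 0.8 × 2.236 = 1.789, and power is 39.5%. A true 0.8 SD difference would therefore be missed 100 − 39.5 = 60.5% of the time.

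| Split | Power at 0.8 SD | Difference with 80% power |
|---|---|---|
| 10/10 | 39.5% | 1.32 SD |
| 8/12 | 38.2% | 1.35 SD |
| 6/14 | 34.2% | 1.45 SD |

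At 10/10, power for other effects is:

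| True difference | 1.0 SD | 1.2 SD | 1.5 SD | 2.0 SD |
|---|---|---|---|---|
| Power | 56% | 72% | 89% | 99% |

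The conclusion does not depend on the choice of test or on dropout. A simulated Mann–Whitney test at 10/10 has about 35% power at 0.8 SD. All 24 enrolled patients, split 12/12, would have given 46.6%. Reaching 80% power at 0.8 SD takes 26 per arm.

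**Keratinized gingiva width, 10/10, Bonferroni-corrected.**

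| Divisor | Alpha | t_crit | Power at 0.8 SD | Power at 1.3 SD | Difference with 80% power |
|---|---|---|---|---|---|
| 2 | 0.025 | 2.445 | 28% | 68% | 1.48 SD |
| 4 | 0.0125 | 2.775 | 19.5% | 56% | 1.64 SD |
| 5 | 0.01 | 2.878 | 17% | 53% | 1.69 SD |
| 13 | 0.0038 | 3.316 | 10% | 38% | 1.89 SD |

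At 1.3 SD the primary endpoint has 78% power, but keratinized width has 38% to 68%. At 10/10, one statement at the 80% level covers both outcomes only if large means at least 1.48 to 1.89 SD, depending on the divisor.

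**The case against.** The strongest reply is that the SAP never says 0.8 SD. That threshold is brought in from outside, and the plan states no figure that the calculation could contradict. If the authors meant about 1.3 SD or more, the sentence is true for the primary endpoint at an even split. The procedures differ markedly, one a limited elevation without vertical releasing incisions and the other a full-thickness flap advanced coronally. Nothing in the documents rules out an expected effect of that size on vestibular depth. This stands. A reader might infer that the statement is simply false or contains an arithmetic error; the documents do not support that. They support calling it unquantified, and wrong under the conventional meaning.

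The second reply concerns the secondary endpoint. A reader might take the five secondary bullets as the divisor and conclude that power for keratinized width is 17% or less. The SAP gives no divisor, and 4 or 2 are possible readings, with 19.5% and 28%. This also stands, although power is far below 80% under every reading.

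Third, the plan calls secondary results supportive and lists small sample size under Protocol Limitations. It nowhere says that a null soft-tissue result will be read as evidence of no large difference. That lowers the risk of misreading but does not remove it. The limitations section reserves its hypothesis-generating label for bone findings, which leaves the contrast between adequate soft-tissue sensitivity and inadequate density sensitivity in place.

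**Conclusion.** The concern holds in a limited form. The statement of adequate sensitivity has no effect size, SD, target power or arm sizes behind it, and it is wrong if large means 0.8 SD. Under that assumption, power for the primary endpoint is at most about 40%. The smallest difference with 80% power is about 1.32 SD at best, rising to 1.45 SD at 6/14. For keratinized width at 10/10, power at 0.8 SD lies between 10% and 28%, depending on an unstated divisor.

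The detectable differences need no view on what large means. They rest on the t test, the two-sided alpha, the split, the divisor and an 80% benchmark. Only the word wrong depends on 0.8 SD.

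This should be fixed, but it is not critical: enrolment is closed, no test, alpha or analysis set changes, and small sample size is already acknowledged in general terms.

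**What to change.** Replace the soft-tissue part of the Power considerations sentence with:

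> With 20 completers (at best 10 per arm) the study has 80% power only for a difference of about 1.3 SD or more in the primary endpoint (about 40% for 0.8 SD), and about 1.5 to 1.9 SD for Bonferroni-corrected soft-tissue endpoints, depending on the divisor. These figures were computed after enrolment.

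Then:

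1. Give the actual arm sizes and the Bonferroni divisor, and reduce the ranges to the figures that apply.
2. Give the detectable difference in mm, as the multiple of the SD of change, naming the SD used and its source. The documents give no SD for vestibular depth or keratinized width.
3. State that a non-significant soft-tissue result does not exclude a large difference and is to be interpreted from its 95% confidence interval.

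The cost is one paragraph of wording and no extra patients. The stated sensitivity becomes less favourable.

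### The only serious-event statement covers events judged related, is not split by arm, and may leave out the four non-completers (minor)

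*Combined protocol and SAP*

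**What the plan says.** The Safety Monitoring section describes broad surveillance: "Participants were monitored at each follow-up visit for adverse events, including infection, dehiscence, hematoma, epistaxis, persistent OAC, fistula formation, and signs of maxillary sinusitis". It adds "All complications were recorded prospectively" and then gives its single result for serious events: "No serious adverse events related to the interventions were reported". That sentence has no denominator, no breakdown by arm and no interval. The documents define neither seriousness nor relatedness and do not say who assessed relatedness.

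On numbers, Study Population and Enrollment says: "Twenty-four patients were enrolled; twenty completed the full 90-day follow-up and were included in the final analysis". The SAP text on missing data says: "Only participants who completed the 90-day follow-up were included in the final per-protocol analysis", and "No imputation of missing values was performed". No separate safety population is defined, and arm sizes are not given.

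Under Outcome Measures, the incidence of postoperative complications is a secondary endpoint. It names seven events: swelling, hematoma, epistaxis, dehiscence, persistent communication, fistula and clinical sinusitis. It is not filtered by relatedness or graded for seriousness. The SAP summarises categorical variables as counts and proportions.

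**The concern.** Two restrictions can each remove a serious event from the summary. The first is the relatedness filter. An event judged unrelated does not appear in the only serious-event statement, and if it also lies outside the seven listed complications, the plan gives it no other place to appear. The second is the completers-only population. If the safety count follows the SAP's analysis set, a patient who left before day 90 is not counted, and leaving may itself be linked to a bad outcome.

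This matters because lower postoperative morbidity with the membrane is part of the study hypothesis, so harms by arm bear on the main question. Allocation was not random: "Participants were assigned to one of two parallel treatment arms based on a predefined clinical protocol and the availability of the membrane technique". One operator treated everyone: "All surgical procedures were performed by the same experienced oral surgeon to minimize operator-related variability". A full count by arm does not repair confounding, but it does not depend on an individual causality judgement, and it lets a reader see whether events cluster in one arm. A related-only statement pooled over arms does not.

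**Working it through.** **Inputs from the documents.** Enrolled 24 and completers 20 (Study Population and Enrollment); analysis set of completers only (SAP, missing data); zero related serious events, denominator not stated (Safety Monitoring). The plan gives no safety rate, interval or safety sample size, so there is no figure of its own to reproduce.

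**Assumption.** Arm sizes are not given. I use 12 per arm (24 enrolled, split equally) and 10 per arm (20 completers, split equally), with a range of 8 to 16.

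**Step 1: share of patients whose safety status is unclear.** 24 − 20 = 4, and 4/24 = 16.7%. If the zero refers to completers only, the count among all enrolled could lie anywhere from 0/24 to 4/24. The exact two-sided 95% upper limit is 14.2% for 0/24 and 37.4% for 4/24.

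**Step 2: what a zero count can exclude.** For 0 events in n patients, the exact (Clopper-Pearson) two-sided 95% upper limit is 1 − 0.025^(1/n).

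| n | Basis | Upper limit |
|---|---|---|
| 24 | all enrolled | 1 − 0.025^(1/24) = 14.2% |
| 20 | completers | 1 − 0.025^(1/20) = 16.8% |
| 12 | per arm, assumed | 1 − 0.025^(1/12) = 26.5% |
| 10 | per arm, assumed | 1 − 0.025^(1/10) = 30.8% |
| 8 to 16 | per arm, assumed range | 36.9% down to 20.6% |

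**Step 3: how often zero would occur at a non-trivial risk.** With a true risk of 5% (illustrative), the probability of no events is 0.95^n: 0.95^24 = 29% and 0.95^20 = 36%. In one arm, 0.95^12 = 54% and 0.95^10 = 60%.

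**Step 4: which event type these limits describe.** The document reports zero only for related serious events. The all-cause serious count is not stated and may not be zero. The limits in Step 2 apply to whichever count is truly zero, and must not be carried over to all-cause events until that count is known.

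**Step 5: how far the complications endpoint closes the gap.** It is unfiltered, so a listed complication is captured whatever its presumed cause. Three gaps remain. A serious event outside the seven is not in it; infection, for example, is monitored under Safety Monitoring but is not among the seven. Severity is not recorded in the endpoint. The only population to which it could be applied, as written, is completers.

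**The case against.** The strongest reply is that the plan does count harms without a causality filter. Surveillance at every visit is open-ended, all complications were recorded prospectively, and their incidence is a secondary endpoint shown as counts and proportions in a two-arm study. That stands. A reader might infer that the relatedness filter removes the comparison of harms between arms, but the filter governs one sentence only.

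Three other strong readings also go beyond the text:

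- A reader might take the sentence as a conclusion that the techniques are safe. The documents draw no such inference. It is a one-line report that openly states its restriction to related events, and the limitations section acknowledges the small sample and short follow-up, although the consequence it spells out concerns bone findings only.
- A reader might infer that the surgeon, or someone else aware of the technique, judged causality. The documents do not say who did. They list a blinded clinical assessor but tie that role to probe measurements. The assessor is unspecified, and no more can be claimed.
- A reader might take the upper limits as a fault in the plan. They follow from any zero count in a study of this size. They limit what the count can support and do not show an error.

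It is also fair to say that the 24-versus-20 question comes from the general completers-only rule and is not peculiar to safety. The documents do not state that the serious-event sentence excluded the four non-completers; they leave it open. What survives is that serious events judged unrelated, and events in non-completers, have no assured place in the reported safety data.

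**Conclusion.** The point holds as a minor reporting weakness. The serious-event summary is limited to related events, is not split by arm, and has no stated denominator, while up to 4 of 24 patients (16.7%) may fall outside it. The complications endpoint reduces the gap but does not close it. A zero count would still be compatible with a risk of up to 14.2% in 24 patients or 16.8% in 20. Per arm the limit is roughly 26% to 31% if there were 12 or 10 patients in each, which is an assumption. Whether any serious event was in fact left out cannot be determined from the documents. The primary endpoint is not affected, and no conclusion stated in the documents depends on this sentence.

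**What to change.** Replace the sentence with a table of all serious adverse events regardless of relatedness, together with the seven listed complications, by arm for all 24 enrolled patients, each followed to last contact. Give the numerator, denominator and exact 95% confidence interval in every cell, and show the relatedness judgement as a secondary column, with a note of who made it. State the length of follow-up and any known events for the four non-completers.

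If the all-cause serious count is zero, give the upper limit (14.2% for 0/24, and the per-arm limits from the actual arm sizes) and draw no conclusion of equal or acceptable serious risk. If it is not zero, report the observed count with its interval.

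The cost is one extra table and a few sentences. Complications were recorded prospectively, so most of the data should exist; serious events outside the listed complications, and the non-completers' records to last contact, would need checking. The downside is a slightly less favourable safety statement.
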